10.1 Definition of Adverse Events/Severe Adverse Events

10.1.1 Adverse events as defined in the International Council on Harmonisation Guideline for Good Clinical Practice are described as: “an untoward medical occurrence in a patient or clinical investigation administered a pharmaceutical product that does not necessarily have a causal relationship with this treatment” (ICH E6:1.2).

10.1.2 A serious adverse event is an adverse event that:

- is fatal
- is life threatening (places the subject at immediate risk of death)
- results in inpatient hospitalization or prolonged existing hospitalization
- results in persistent or significant disability/incapacity

- is a congenital anomaly/birth defect
- other significant hazard

10.2 Reporting of Adverse Events

10.2.1 The principal investigator at each site is responsible for reporting each adverse event to the Protocol Chairman or the study nurse/coordinator coordinating site (Ohio State University Hospital). Contact information is provided in section 16.0 of the study protocol. Adverse events must be reported verbally and faxed to the coordinating site within 7 days of the occurrence using the supplied "Adverse Event" form (see Appendix 3). All serious adverse events must be communicated to the coordinating site verbally within the first 24 hours of the occurrence of the event. The "Adverse Event" form (see Appendix 3) must also be completed and returned to the coordinating site within 7 days of the occurrence of the event. Using these mechanisms of rapid reporting we will be able to rapidly evaluate and minimize the potential risks to patients from the occurrence of these events. Any significant adverse events that potentially would affect other enrolled patients and those yet to be enrolled will be communicating to all participating sites and investigators in a written format and via teleconference if warranted.

10.3 Follow-up of Adverse Events

10.3.1 Patients experiencing an adverse event will continue to be followed and carefully monitored until the resolution of the adverse event. This applies whether the patient continues on study or is removed from the study for any reason.

11.0 Sample Procurement

11.0.1 As stated in section 9.0, both plasma and blood samples will be taken as a part of this protocol. These samples will be obtained at the same time that standard clinical samples or procedures are being performed so patients will not be exposed to additional venipunctures or procedures by their participation in this study. The plasma to be studied is the byproduct of the plasma exchange procedure and would otherwise be discarded. Instead of discarding the entire plasma sample, 100 cc will be collected for study as is described in the protocol.

11.2 Sample Utilization

11.2.1 As our understanding of the pathophysiology of TTP increases, we will likely discover additional proteins or molecules that play a role in the initiation or the progression of TTP. It is for this reason that we will bank samples for future study. The patient samples held in storage will be kept indefinitely or until the sample is completely utilized for correlative studies. The patient samples will only be studied at the Ohio State University and will not be shared with any other researcher for study without prior approval of the IRB. The subject may withdraw consent at any time and the sample remaining and any data will be destroyed to the extent that is possible. Patients also will not receive any financial gain from the research associated with the tissue sample research or its applications.

12.0 Risks Associated with Testing of Patient Samples

12.1 A breach of confidentiality is the most serious risk which patients may be exposed to regarding to the testing of biologic samples. Confidentiality will be maintained by labeling the patient samples with only an identification number and not their name or medical record number. By using this approach, patient samples may be tied to clinical information by the investigators but will preserve the confidentiality of patients. Only the principal investigator, co-investigator, and the study nurse/coordinator will have access to both the study number and the corresponding patient identification information. Clinical information or laboratory data used for publication will not identify patients in any way that could potentially breach patient confidentiality.

13.0 ADAMTS13 Assays and ADAMTS13 Inhibitor Assays

13.1 Novel SELDI-Based ADAMTS13 Assay

[name] laboratory has invested tremendous efforts to validate and standardize the tests for ADAMTS13 activity and inhibitory titer to meet the requirements set forth by the College of American Pathologists (CAP) for clinical testing. Both tests are done using a SELDI-TOF mass spectrometer. Validation studies were performed to evaluate test accuracy, test precision, reportable range, and test linearity. For example,

test accuracy was partly evaluated by testing a set of unknowns and correlating the results with those from the Coagulation Reference Laboratory at the BloodCenter of Wisconsin (Kindly supported by [name]). Excellent correlation was achieved between SELDI-TOF and the FRET assays for ADAMTS13 (activity and inhibitor titer). ADAMTS13 activity and inhibitor titer assays are now offered as clinical tests at OSUMC and are performed under SOPs with QC reagents (normal and abnormal) included in each run to ensure test accuracy. Longitudinal evaluation of QC samples is performed to monitor the test reproducibility and analytical performance of the instrument.

In late 2005, [name] laboratory started using the SELDI-TOF mass spectrometry-based method to determine ADAMTS13 activity in patient samples (49). This new test offers a rapid result within 4 hours and has excellent test reproducibility (6, 42, 49, 50). In 2008, [name] laboratory modified the SELDI-TOF assay to now detect as low as 0.5% of ADAMTS13 activity in clinical samples (51). With this improvement we now can more precisely measure ADAMTS13 activity in most samples with extremely low activity. This in turn provides a dataset with quantifiable values in >95% of TTP samples to help for statistical analysis.

13.2 Laboratory Method for ADAMTS13 Antigen and Antibody (IgG) Concentrations

Quantification of ADAMTS13 antigen and ADAMTS13 autoantibody (IgG) will be measured using commercially available ELISA kits from American Diagnostica Inc. (IMUBIND® ADAMTS13 ELISA and ADAMTS13 Autoantibody ELISA). These two kits have been validated in our laboratory and used for several studies (6, 42, 49, 50). The reference ranges for both kits were determined using healthy donors (n=41) recruited from the local population. The results for the autoantibody ELISA are reported as micrograms of IgG antibody and for ADAMTS13 antigen reported as nanograms of ADAMTS13 protein per milliliter of patient plasma respectively.

13.3 Laboratory Method for ADAMTS13 Inhibitor Titer Determination

In order to evaluate ADAMTS13 inhibitory titer, we set up a SELDI-TOF based test for the determination of inhibitory titer as Bethesda units (BU). BU in each sample is defined as the dilution of patient plasma that neutralizes 50% of ADAMTS13 activity in an equal volume of pooled normal plasma (PNP). This method is similar to the standard laboratory procedure for the determination of BU for clotting factors that requires 1 hour incubation after mixing patient plasma (or dilute) with PNP(52).**13.4 Laboratory Method for VWF multimeric analysis:**

VWF multimeric analysis will be performed in Biomarker Reference Laboratory at the Ohio State University Medical Center. [name] is the

director of this clinical laboratory. The cost for this test will be paid from research fund under this clinical trial study.

14.0 Statistical Analysis

14.1 Statistical Considerations-Sample Size Determination

For the study of the primary endpoint (treatment success rate), the sample size required is calculated based on the data from our previous publications. In these previous studies that looked separately at CSA/PE in 10 patients and at corticosteroids/PE in another 10 patients, we saw promising results that led to our hypothesis that CSA/PE treatment for TTP patients results in greater treatment response. In those studies, the primary endpoint was the proportion of patients who had TTP exacerbation, which is a more stringent endpoint that does not include other types of treatment failures such as refractory patients and/or death within 30 days post-PE. In the previous published pilot studies, we showed that 6/10 corticosteroid-treated patients exacerbated versus 0/10 CSA-treated patients. Combined with experience with subsequently treated patients, we observed an overall treatment success rate of 80% and 83% in refractory vs. de novo TTP patients, respectively, treated with CSA+PE versus 33% in those treated with corticosteroids+PE.

In terms of our primary endpoint of treatment success rate, we have designed a phase III trial that compares the proportion of treatment successes in each arm. Specifically, this study design will have at least 80% power to determine a significant difference in the treatment success rates between the arms if the true rates are 50% vs. 80%, assuming a significance level of 0.05 and a two-sided test. This reflects a clinically meaningful difference, and the data from our previous studies and experience support it as a feasible difference to detect. We plan to enroll a total of 72 patients to this trial (36 to each arm) to test the null hypothesis that there is no difference in treatment success rate between these treatments.

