5.0 Patient Selection

5.1 Inclusion of Women and Minorities.

Entry to this study is open to both men and women ages 18 and older, of all racial and ethnic subgroups. This study will be conducted in accordance with the International Conference on Harmonisation and the Helsinki Guidelines.

5.2 Eligibility Criteria.

- 5.2.1 Patients with a clinical diagnosis of idiopathic TTP as defined by a microangiopathic hemolytic anemia and thrombocytopenia ($<100 \times 10^3$)
- 5.2.2 Additional components of the pentad (fever, renal and neurologic abnormalities) need not be present.
- 5.2.3 Additional explanations for the microangiopathic changes including DIC and malignancy should be excluded.
- 5.2.4 Patients with pregnancy associated TTP will be permitted on this therapeutic trial if the child is delivered prior to the initiation of therapy for TTP. However, female patients that are breastfeeding and are unwilling to discontinue breastfeeding at the time of enrollment will be excluded from this study (see section 5.3.5)
- 5.2.5 Patients with a previous diagnosis of TTP are eligible to be enrolled provided they meet eligibility criteria and have not been treated for TTP in the past 30 days.
- 5.2.6 Given the potential for nephrotoxicity with CSA, all patients must have a serum creatinine of ≤ 2.5 mg/dl prior to enrollment

5.3 Exclusion Criteria.

- 5.3.1 In light of concern for the prompt initiation of PE, all patients with suspected TTP may be enrolled on this trial. If it is subsequently found that the patient does not meet enrollment criteria, they will be removed and their spot replaced for study purposes. Patients removed from the

study after enrollment will continue to be followed longitudinally for 6 months to be monitored for safety and will be included in the safety database.

- 5.3.2 Patients with TTP clinically categorized as secondary to stem cell transplant and solid organ, bloody diarrhea associated, malignancy associated, and drug associated will not be enrolled on this therapeutic study.
- 5.3.3 Incarcerated patients will be excluded from the study due to the inherent difficulties in maintaining close follow-up for study purposes in patients who are incarcerated.
- 5.3.4 Any patients already being treated chronically with corticosteroids or cyclosporine and taking these at the time of their presentation will be excluded from this study.

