6.0 Randomization of Patients

6.1 Patients will be randomized at the time of registration/enrollment on this clinical trial via contact with the study nurse/coordinator at the time of the initial registration of the subject. The study statistician ([name]) will conduct the randomization and relay this information to the study nurse who will be in contact with the treating/enrolling physician so that the appropriate medication (prednisone or cyclosporine) may be immediately started with PE.

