14.2 Analysis Plan

Patients will be followed for 30 days after their last PE procedure unless a treatment failure has been documented prior to that timepoint. The treatment success rates will be calculated for each of the treatment arms along with their 95% confidence intervals. These proportions will be compared between treatment arms using Mantel-Haenszel chi-square test to accommodate the

stratification factor (recurrent vs. de novo TTP event). Statistical significance will be concluded based on a significance level of 0.05.

This study includes an interim analysis and formal “look” at the data after 24 patients have been accrued (12 to each arm), where the null hypothesis will be rejected if the calculated p-value comparing the two observed success rates for the treatment arms is <0.0002 (based on the Lan-DeMets alpha spending function and O’Brien-Fleming boundary calculation). We will also evaluate safety and tolerability data for each of the arms at the interim analysis, and these data will be reviewed not only by the study team but by the DSMB.

Through this study we also planned an internal pilot study to be completed after 12 patients have been accrued (6 to each arm) in an effort to obtain information on the feasibility of accrual and treatment follow-up for the endpoints; as an internal pilot study, all patients will be included in the overall trial and thus included in the interim and final analyses unless serious logistical issues were identified that would introduce bias by their inclusion. We reached the accrual point for this internal pilot study and no such logistical issues were identified; therefore, all patients will be included in the overall study. With so few patients, this internal pilot was used for assessment of feasibility; the early data were not formally evaluated and did not require a re-evaluation of our assumptions for the study design described above.

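### The promised minimum of 80% power at 36 per arm matches the unpooled-variance formula; the planned Mantel-Haenszel test, uncorrected, has about 77% when the two strata have similar success rates

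*Combined protocol and SAP*

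**What the plan says.** Section 14.1 sets the size of the trial: "We plan to enroll a total of 72 patients to this trial (36 to each arm"). It justifies this by stating that "this study design will have at least 80% power to determine a significant difference in the treatment success rates between the arms". The assumptions behind that figure are success rates of 50% in one arm and 80% in the other, tested two-sided at the 0.05 level. The section names no formula or software and does not tie the power figure to a particular test.

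The deciding test is given in section 14.2: "These proportions will be compared between treatment arms using Mantel-Haenszel chi-square test". The analysis is to allow for one factor, named there as the "stratification factor (recurrent vs. de novo TTP event"). Neither section gives the expected share of recurrent patients or separate success rates for the two strata, and 14.2 does not say whether a continuity correction applies. Section 6.0 describes how allocation is done ("Patients will be randomized at the time of registration/enrollment on this clinical trial via contact with the study nurse/coordinator") but does not mention allocation within strata.

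**The concern.** The power is stated as a minimum and is attributed to the design, so it should hold for the test the design uses. The unpooled-variance formula scales the difference by its variance under the alternative. A Mantel-Haenszel test takes its variance under the null hypothesis, which is larger at 50% versus 80%. A sample size from the first can therefore fall short under the second.

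This figure is the only justification given for 72 patients. If the final result is not significant, a reader will judge it against a type II error of at most 20%, and should be told the error rate of the test that was run.

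**Working it through.** **Inputs.** From 14.1: success rates 0.50 and 0.80, two-sided alpha 0.05, 36 per arm. From 14.2: Mantel-Haenszel test, two strata. The documents do not give stratum shares, stratum rates or the balance of strata between arms, so these are varied below.

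**Step 1: reproduce the plan's figure.** With unpooled variance,

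n = (1.960 + 0.8416)² × (0.50×0.50 + 0.80×0.20) / 0.30² = 35.76, rounded up to 36.

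Power at 36: 0.30 / √(0.41/36) = 2.811; 2.811 − 1.960 = 0.851; Φ(0.851) = 80.3%. This matches both the 36 per arm and the 80% minimum.

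**Step 2: the same calculation with the null variance.** The pooled rate is 0.65, so the null variance term is 2 × 0.65 × 0.35 = 0.455.

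n = (1.960 × √0.455 + 0.8416 × √0.41)² / 0.30² = 38.48, so 39 per arm.

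Power at 36: [0.30 − 1.960 × √(0.455/36)] / √(0.41/36) = (0.3000 − 0.2203) / 0.1067 = 0.746; Φ(0.746) = 77.2%.

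Two other two-sided approximations also miss at 36: arcsine gives 77.9%, and pooled variance under both hypotheses gives 76.1%.

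**Step 3: exact enumeration at 36 per arm, no strata.**

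| Test | Power, 50% vs 80% | Type I error, 65% vs 65% |
|---|---|---|
| Unpooled Wald | 80.5% | 6.2% |
| Pearson chi-square | 78.7% | 5.3% |
| Mantel-Haenszel, uncorrected | 77.2% | 4.8% |
| Mantel-Haenszel, continuity-corrected | 69.6% | 2.7% |

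The Wald test that corresponds to the unpooled formula reaches 80% partly by exceeding the 5% level. The Mantel-Haenszel variance has N − 1 in place of N, so its statistic is the Pearson chi-square times 71/72; this accounts for the gap between those two rows. Exact uncorrected Mantel-Haenszel power is 79.97% at 38 per arm and 80.2% at 39.

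**Step 4: the stratified test.** Overall rates are held at 50% and 80%. The gap is the difference in control-arm success rate between the strata. Assumption: the lower-success stratum holds 20 to 50% of patients. As 6.0 does not describe stratified allocation, two cases are shown: stratum counts equal in both arms (exact; 7 to 18 of 36 per arm in the lower stratum) and stratum counts left to chance (simulation, 400,000 runs per cell, standard error 0.0007).

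| Gap between strata | Counts left to chance | Counts equal by arm |
|---|---|---|
| 0 points | 76.8–77.1% | 77.4–77.6% |
| 5 points | 77.0–77.2% | 77.5–77.8% |
| 10 points | 77.2–77.7% | 77.7–78.3% |

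**Step 5: how large a gap restores 80%?** Smallest control-arm gap giving at least 80%, in steps of one point, under the same share assumption:

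| | Common risk difference | Common odds ratio |
|---|---|---|
| Counts equal by arm | 20–26 points | 24–29 points |
| Counts left to chance | 24–29 points | 30–33 points |

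If the lower-success stratum is the majority (60 to 80% of patients; counts left to chance, common odds ratio), the threshold rises to 31–40 points.

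**Step 6: what the design does support.** At 50% versus 81%, uncorrected Mantel-Haenszel power is 80.4% (exact, unstratified). With equal stratum rates it is 80.2–80.3% when counts are left to chance and 80.6–80.8% when they are equal by arm.

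**Interim look.** Rejecting at p < 0.0002 after 24 patients moves the final critical value only from 1.960 to 1.961, so it does not explain the gap.

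**The case against.** Several points can be made for the plan.

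- *The formula is inferred.* This is true: 14.1 names none. The match on both 36 per arm and 80.3% is close, but it remains an inference. The power of the planned test does not depend on it.
- *Stratification can recover the power.* Calling the factor a stratification factor suggests that it was thought prognostic, and a large enough gap does restore 80%. But that takes at least 20 points, and the documents offer no evidence of one. The 80% and 83% success rates in 14.1 cannot settle the matter either way. They compare refractory with de novo patients, whereas section 5.2.5 admits previously diagnosed patients only if they "have not been treated for TTP in the past 30 days". So what is shown is that the minimum is not assured and fails for similar strata, not that it fails for every possible population.
- *The version of the test matters more than this gap.* This stands. A continuity correction would lower power to about 68–70%. The calculation here uses the uncorrected version, which is the more favourable one for the plan.
- *Part of the gap is discreteness.* Exact uncorrected Mantel-Haenszel power is 77.1% at 35 per arm, 77.2% at 36 and 78.6% at 37, and the stratified figure with equal counts is nearer 78%. This is fair, but none of these figures reaches 80%.
- *The consequence is slight.* Also fair. Against the earlier experience quoted in 14.1 (33% success on corticosteroids, 80–83% on cyclosporine), 50% versus 80% is a cautious assumption; at 33% versus 80% the uncorrected test has 98.7% power. The statement in the plan is nevertheless made for 50% versus 80%.

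**Conclusion.** The concern holds, and it is minor. At 36 per arm and 50% versus 80%, the uncorrected Mantel-Haenszel test has 77.2% power unstratified and 76.8–77.8% stratified when stratum rates are 0 to 5 points apart. Type II error is then about 22–23%, not at most 20%. The stated minimum is met only if the strata differ by roughly 20–33 points when the lower-success stratum is 20–50% of patients, and by up to about 40 points when it is the majority. The result assumes no continuity correction; with one, the shortfall would be larger. It does not put the sample size or the choice of test in question.

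**What to change.** Keep 72 patients and the planned test. Replace the power statement in 14.1 with wording such as: *approximately 77% power for 50% versus 80% with the planned Mantel-Haenszel test without continuity correction, assuming similar success rates in the two strata (about 80% for 50% versus 81%)*. In the same place, name the formula that gave 36 per arm. Because 14.2 is silent on continuity correction, the sponsor should confirm that the uncorrected version is intended; the restated figure applies only to that version.

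The cost is one reworded sentence and a slightly less favourable power figure. No extra patients are needed.

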14.2 Analysis Plan

Patients will be followed for 30 days after their last PE procedure unless a treatment failure has been documented prior to that timepoint. The treatment success rates will be calculated for each of the treatment arms along with their 95% confidence intervals. These proportions will be compared between treatment arms using Mantel-Haenszel chi-square test to accommodate the

stratification factor (recurrent vs. de novo TTP event). Statistical significance will be concluded based on a significance level of 0.05.

This study includes an interim analysis and formal “look” at the data after 24 patients have been accrued (12 to each arm), where the null hypothesis will be rejected if the calculated p-value comparing the two observed success rates for the treatment arms is <0.0002 (based on the Lan-DeMets alpha spending function and O’Brien-Fleming boundary calculation). We will also evaluate safety and tolerability data for each of the arms at the interim analysis, and these data will be reviewed not only by the study team but by the DSMB.

Through this study we also planned an internal pilot study to be completed after 12 patients have been accrued (6 to each arm) in an effort to obtain information on the feasibility of accrual and treatment follow-up for the endpoints; as an internal pilot study, all patients will be included in the overall trial and thus included in the interim and final analyses unless serious logistical issues were identified that would introduce bias by their inclusion. We reached the accrual point for this internal pilot study and no such logistical issues were identified; therefore, all patients will be included in the overall study. With so few patients, this internal pilot was used for assessment of feasibility; the early data were not formally evaluated and did not require a re-evaluation of our assumptions for the study design described above.

Additionally, we will evaluate several secondary clinical endpoints through this trial, including: 1) exacerbation rate within 30 days post-PE; 2) clinical response rate; 3) the number of PE procedures required to achieve a clinical response; 4) relapse rate; and 5) safety and tolerability of each of the adjuvant treatments to PE. Each of the rates will be calculated assuming that these endpoints are binomially distributed, and 95% confidence intervals generated. For the exacerbation rate endpoint, we will only include those patients who have achieved clinical response (i.e. excluding refractory patients) and compare these rates between the two arms. We will have at least 80% power to detect a difference if the true exacerbation rates are 55% vs. 90% for this subset analysis (not adjusting for multiple comparisons); however, this comparison is distinctly ancillary to our primary clinical interest of achieving treatment success in all patients treated versus only keeping responding patients from experiencing TTP exacerbation. We will also evaluate relapse as a time-to-event variable, where Kaplan-Meier methods will be used to assess time to relapse from last plasma exchange in responding patients. The number of exchange procedures required to achieve clinical response will be assessed between arms using Poisson regression. Safety and tolerability data will be summarized by type of adverse event with frequencies calculated and compared between arms. In addition to these planned quantitative analyses, we will also use graphical

analyses to assess patterns and differences in these factors between the treatment arms.

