1.0 OBJECTIVES

This will be a multi-center, open-label, randomized study that directly compares the use of cyclosporine and plasma exchange to corticosteroids and plasma exchange as the initial treatment of patients with thrombotic thrombocytopenic purpura. This study has the following objectives:

Primary Objective

1.1 To determine if cyclosporine given individually as an adjunct to plasma exchange decreases the rate of exacerbation in patients with TTP compared to corticosteroids given as an adjunct to plasma exchange.

Secondary Objectives

1.2 To compare the CSA and PE treatment arm to the corticosteroid and PE treatment arm with respect to:

- exacerbation rate within 30 days post-PE
- clinical response rate
- number of exchange procedures to achieve clinical response
- relapse rate (recurrent disease >30 days after last PE)
- safety data for CSA as an adjunct to PE.
- the effects of corticosteroids vs. cyclosporine on ADAMTS13 antigen, activity, and ADAMTS13 antibody concentration and inhibitor titers using serial measurements both during and after discontinuation of study drug
- the VWF multimeric patterns after initial therapy and throughout longitudinal follow-up between the two treatment arms
- the laboratory biomarker(s) that are prognostic for TTP exacerbation and the risk of relapse

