8.4 Exacerbation/Relapse Determination

8.4.1 Criteria to determine recurrences of disease and the need for re-initiation of therapy with plasma exchange will be the same as those to diagnose TTP (section 5.2.1). Patients requiring the reinstitution of plasma-based therapy (plasma exchange or infusion) within the first 30 days after discontinuing PE will be considered to have an “exacerbation” of their TTP.

8.4.2 Patients with a recurrence of TTP at a time point greater than 30 days from the end of plasma exchange therapy will be considered to have a "relapse" for the purposes of this study.

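### Section 14.2 sends by-arm interim safety data to the study team and leaves access to the by-arm success rates unrestricted, in an open-label trial whose endpoint rests partly on clinical judgement

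*Combined protocol and SAP*

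**What the plan says.** Section 1.0 describes a "multi-center, open-label, randomized study". Section 14.1 sets the size: "We plan to enroll a total of 72 patients to this trial (36 to each arm"). Section 14.2 places one formal efficacy look "after 24 patients have been accrued (12 to each arm"), with rejection at p < 0.0002. It goes on to say that safety and tolerability will be evaluated for each arm at that look, and that "these data will be reviewed not only by the study team but by the DSMB".

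The section does not say who sees the by-arm success rates. The text available describes no DSMB-only report, no independent statistician for the interim, no limit on release of interim results and no masked adjudication of outcomes. Under section 6.1 the study statistician conducts the randomization and passes on the assignments.

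The outcome rules that matter here are these:

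- **Exacerbation (8.4.1):** "Patients requiring the reinstitution of plasma-based therapy (plasma exchange or infusion) within the first 30 days after discontinuing PE" are counted. The criteria for recurrence and for restarting exchange are those used for diagnosis in 5.2.1.
- **Refractory disease (8.3.1):** no sign of improvement or benefit after one week, with no numeric threshold; the patient counts as having failed therapy.
- **Remission (8.1):** platelet count, LDH, creatinine relative to enrolment, and improvement in neurologic findings.
- **Removal after enrolment (5.3.1):** if patients turn out not to meet the enrolment criteria, "they will be removed and their spot replaced for study purposes".

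**The concern.** In an open-label trial, clinicians already know which drug each patient takes. What can still be withheld from them is how the arms compare in aggregate. Section 14.2 gives part of that comparison (safety and tolerability) to the study team and does not protect the rest.

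Someone who has seen the arms compared may, without intending it, lean one way on a borderline refractory call, a neurologic assessment, the threshold for restarting plasma therapy, or the scrutiny given to a patient's eligibility after enrolment. The first three feed the primary endpoint, and the last decides who is analysed. At stake is the freedom from bias of the comparison among patients enrolled after the look.

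**Working it through.** **1. The plan's interim boundary.** The information fraction is 24/72 = 1/3. With O'Brien-Fleming-type Lan-DeMets spending applied to each 0.025 tail, the two-sided alpha spent is

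4 × [1 − Φ(z(0.9875)/√(1/3))] = 4 × [1 − Φ(2.2414/0.5774)] = 4 × [1 − Φ(3.882)] = 0.00021.

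This reproduces the stated 0.0002.

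**2. How often the look ends the trial.** With 12 per arm and a pooled two-proportion z-test, p < 0.0002 requires success counts of 0 vs at least 9, 1 vs at least 11, 2 vs 12, or 3 vs 12. Summing the binomial probabilities of these outcomes, in both directions, gives:

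| True success rates | Source | Chance of stopping |
|---|---|---|
| 50% vs 80% | design rates, 14.1 | 0.6% |
| 33% vs 83% | prior experience, 14.1 | 6.2% |

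The trial therefore almost always continues.

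**3. How many patients follow.** (72 − 24)/72 = 48/72 = 67%, or 24 per arm. Some of the first 24 may also still be inside their 30-day window after the last exchange, because the look is triggered by accrual.

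**4. What a shift in classification would do (assumption, not a document figure).** Suppose the arms truly have the same success rate p, and a fraction m of successes is called failure, but only among the 24 prednisone patients enrolled after the look.

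- CSA successes: Bin(36, p)
- Prednisone successes: Bin(12, p) + Bin(24, p(1 − m))
- Test: z = (difference in proportions)/√[p̄(1 − p̄) × 2/36], two-sided at 0.05

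For example, with p = 65% and m = 10%, post-look prednisone success is 0.65 × 0.90 = 58.5%. The whole prednisone arm is then expected at (12 × 0.65 + 24 × 0.585)/36 = 21.84/36 = 60.7%, against 65% on CSA. The expected number of patients reclassified is 24 × 0.65 × 0.10 = 1.56.

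Exact enumeration over all 37 × 37 outcomes gives the probability of rejection:

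| True rate, both arms | No shift | m = 10% | m = 15% |
|---|---|---|---|
| 50% | 4.5% | 5.4% | 6.5% |
| 65% | 5.3% | 6.9% | 8.8% |
| 80% | 4.9% | 8.1% | 12.1% |

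The expected number of reclassified patients (24 × p × m) runs from 1.2 (50%, m = 10%) to 2.9 (80%, m = 15%). The enumeration uses an unstratified test in place of the planned Mantel-Haenszel test, because the documents do not give the mix of recurrent and de novo patients. It also ignores the interim look, whose chance of stopping under no difference is below 0.01%.

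**The case against.** **The quoted sentence covers safety only.** Read literally, it refers to the by-arm safety and tolerability data just mentioned. A reader might infer that the plan gives the success rates to the study team. It does not say so; access to them is simply not specified. This objection stands. The type I error figures suppose that clinicians know, or think they know, how the arms compare, so they do not measure the effect of a safety table alone.

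**The endpoint is not purely the team's decision.** Recurrence is tied to the diagnostic criteria, remission to platelet count, LDH and creatinine, and removal to failing the enrolment criteria. A reader might infer that the whole endpoint is discretionary, and the documents do not support that. Judgement remains in the refractory call, the neurologic component, the act of restarting plasma therapy and the scrutiny of eligibility.

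**Aggregate creatinine is not a bias path.** Because creatinine is a remission criterion, one might argue that by-arm creatinine tables bear on remission. The criterion compares each patient's measured value with that patient's own enrolment value, and a table does not alter a laboratory result.

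**A larger inflation is tempting.** Applying the same shift to all 36 prednisone patients at a true 65% gives 8.9% and 13.3%. That includes 12 patients accrued before the look, whose outcomes it mostly could not influence, so those figures overstate the effect.

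**The open label came first.** Expectation bias is possible from the first patient, and section 14.1 already states a strong prior (33% vs 80% to 83% success). This also stands: the interim review adds to the problem and does not create it. The added part is nevertheless the avoidable part.

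**Conclusion.** The point holds in a limited form. Section 14.2 explicitly plans to release by-arm safety data to the study team and leaves release of the by-arm success rates open. The look almost never ends the trial at the design rates, so 67% of patients would be enrolled after comparative results could be known.

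No bias is demonstrated, and its size cannot be taken from the documents. Under the assumed 10% or 15% reclassification after the look, type I error lies between 5.4% and 12.1%, depending on the common success rate, against 4.5% to 5.3% without it. At 50% the effect is slight; at 80% it is material.

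The conclusion assumes that the study team includes people who treat patients or classify outcomes, since the available text does not define the team. It also assumes that no separate DSMB document restricts access. If one does, section 14.2 should refer to it. The change is worth making because it is cheap.

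**What to change.** Replace the sentence in section 14.2 with a rule that by-arm interim efficacy and safety tables go to the DSMB only, and that the study team receives pooled safety data and the DSMB's recommendation. State that individual serious adverse events continue to be reported under section 10.2, which already provides for 24-hour verbal reporting to the coordinating site and for informing all sites of significant events.

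The cost is one sentence, and the DSMB already exists. The downside is that the team does not see comparative safety until the DSMB acts. The change confines knowledge of aggregate results; it does not remove the expectation bias that comes with an open label.
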